6.1.7.1 Management of Increases in ALT

If a subject experiences a post-baseline increase in ALT to $> 5 \times$ ULN and also $> 2 \times$ the baseline value, the subject should have a confirmatory ALT measurement performed. If the ALT increase is confirmed to be $> 5 \times$ ULN which is also $2 \times$ the baseline value, the recommendations below should be followed:

- Complete hepatic questionnaire; evaluate for alternate etiology of ALT elevation; document in the source, update the medical history and concomitant medications eCRF (if applicable), and obtain additional testing as appropriate (e.g., hepatitis B panel, etc.).
- Manage the subject as medically appropriate.
- Repeat ALT, AST, total and fractionated bilirubin, alkaline phosphatase and INR within 1 week. Repeat liver chemistries as indicated until resolution.
- Discontinue study drugs if any of the following is observed at any time:
 - ALT level is $\geq 20 \times$ ULN in the absence of an alternate etiology.
 - Increasing direct bilirubin or INR or onset of symptoms/signs of hepatitis.
 - At the discretion of the investigator.

Alternate management of ALT increases is permitted with approval of the AbbVie TA MD.

6.1.8 Collection of Data Regarding Known AIDS-Associated Opportunistic Infections

HIV-1 infected subjects participating in clinical trials may develop infections typically associated with AIDS. These known AIDS-associated opportunistic infections (OI) are listed in [Appendix D](#).³⁸ The events listed in [Appendix D](#) will be summarized as HIV related events, not as AEs. These OIs will be collected from the time of study drug administration until 30 days following discontinuation of study drug.

6.2 Product Complaint

6.2.1 Definition

A Product Complaint is any Complaint (see Section 6.0 for the definition) related to the biologic or drug component of the product(s).

For a product this may include, but is not limited to, damaged/broken product or packaging, product appearance whose color/markings do not match the labeling, labeling discrepancies/inadequacies in the labeling/instructions (example: printing illegible), missing components/product, or packaging issues.

Any information available to help in the determination of causality to the events outlined directly above should be captured.

6.2.2 Reporting

Product Complaints concerning the investigational product must be reported to AbbVie within 24 hours of the study site's knowledge of the event via the Product Complaint form. Product Complaints occurring during the study will be followed-up to a satisfactory conclusion. All follow-up information is to be reported to AbbVie (or an authorized representative) and documented in source as required by AbbVie. Product Complaints associated with adverse events will be reported in the study summary. All other complaints will be monitored on an ongoing basis.

Product Complaints may require return of the product with the alleged complaint condition. In instances where a return is requested, every effort should be made by the investigator to return the product within 30 days. If returns cannot be accommodated within 30 days, the site will need to provide justification and an estimated date of return.

The description of the complaint is important for AbbVie in order to enable AbbVie to investigate and determine if any corrective actions are required.

7.0 Protocol Deviations

AbbVie does not allow intentional/prospective deviations from the protocol unless when necessary to eliminate an immediate hazard to study subjects. The principal investigator is responsible for complying with all protocol requirements, and applicable global and local laws regarding protocol deviations. If a protocol deviation occurs (or is identified) after a subject has been enrolled, the principal investigator is responsible for notifying Independent Ethics Committee (IEC)/Independent Review Board (IRB) regulatory authorities (as applicable), and assigned Site Monitor and the following AbbVie Team Members:

Primary Contact:

Alternate Contact:

Such contact must be made as soon as possible to permit a review by AbbVie to determine the impact of the deviation on the subject and/or the study. Any significant protocol deviations affecting subject eligibility and/or safety must be reviewed and/or approved by the IEC/IRB and regulatory authorities, as applicable, prior to implementation.

8.0 Statistical Methods and Determination of Sample Size

8.1 Statistical and Analytical Plans

The primary analysis will occur after all subjects have completed the PT Week 12 Visit or prematurely discontinued the study. The data for the primary analysis will be locked after

data cleaning. Data collected after this lock will be added to a new version of the database which will be cleaned and locked at the end of the study.

SAS[®] (SAS Institute, Inc., Cary, NC) for the UNIX operating system will be used for all analyses. All statistical tests and confidence intervals will be two-sided with an alpha level of 0.05. Descriptive statistics will be provided, such as the number of observations (N), mean, and standard deviation (SD) for continuous variables and counts and percentages for categorical variables.

Data across subjects of all genotypes will be combined for analysis, unless otherwise indicated. Analyses will be performed on the intent-to-treat (ITT) population defined as all enrolled subjects who receive at least one dose of study drug, unless otherwise specified. Sensitivity analyses of the primary efficacy endpoint, when applicable, will be performed on the ITT population modified to exclude subjects of multiple genotypes according to the central laboratory or phylogenetic analyses (mITT-GT), and on the mITT-GT population modified to exclude subjects who did not achieve SVR₁₂ for reasons other than virologic failure (mITT-GT-VF).

No data will be imputed for any efficacy or safety analysis except for analyses of SVR endpoints (HCV RNA data) and PRO questionnaires. HCV RNA values will be selected for the analyses of all SVR endpoints (e.g., SVR₄, SVR₁₂, and SVR₂₄) based on defined visit windows. A backward imputation method will be used to impute missing responses for SVR analyses. Imputation of missing responses on PRO questionnaires is described in Section 8.1.3.

8.1.1 Demographics

Demographics, baseline characteristics, study drug exposure, and compliance will be summarized across the set of all subjects for the ITT and mITT population(s).

Demographics include age (continuous; < 65 or ≥ 65 years; < 75 or ≥ 75 years), weight, height, waist circumference, BMI (continuous; < 25, ≥ 25 to < 30, or ≥ 30 kg/m²), sex, race, ethnicity, type of Asian descent, and geographic region. Baseline characteristics will

be summarized as continuous variables (where appropriate) and as categorical variables, including all subgroup variables defined in Section 8.1.2.4, and include HCV genotype and available subtype, prior HCV treatment history, baseline HIV co-infection status, HIV ART at baseline, IL28B genotype (CC, CT, or TT; CC or non-CC), baseline HCV RNA level, baseline homeostasis model of assessment – insulin resistance (HOMA-IR), baseline Child-Pugh score (5, 6, or > 6), tobacco (user, ex-user, or non-user) and alcohol use (drinker, ex-drinker, or non-drinker) status, injection drug use, (yes, within last 12 months; yes, more than 12 months ago; or no), use of stable opiate substitution, history of diabetes, baseline metabolic syndrome, history of bleeding disorders, history of depression or bipolar disorder, history of cardiovascular disease, and use of hepato-protectants at baseline.

Summary statistics (N, mean, median, SD, and range) will be generated for continuous variables (e.g., age and BMI), and the number and percentage of subjects will be presented for categorical variables (e.g., sex and race).

Study drug exposure and compliance will be summarized. Treatment compliance to study drug will be calculated based on the percentage of tablets taken relative to the total tablets expected to be taken. A subject will be considered compliant if the percentage is between 80% and 120%. Compliance will be calculated for each subject and summarized with the mean, median, standard deviation, minimum, and maximum. The percentage of compliant subjects will be calculated based on data as observed. An additional summary of the percentage of compliant subjects will be provided where subjects who are missing study drug accountability records will be imputed as non-compliant.

The summaries described above will also be performed for each geographic region.

8.1.2 Efficacy

All efficacy analyses will be performed on the ITT population, unless otherwise specified.

Plasma HCV RNA levels will be determined by an approved HCV RNA quantitative assay for each sample collected by the central laboratory (including but not limited to Roche COBAS® AmpliPrep/COBAS® TaqMan® HCV Quantitative Test, v 2.0).

8.1.2.1 Primary Efficacy Endpoint

The primary efficacy endpoint is SVR₁₂ (HCV RNA < LLOQ 12 weeks after the last actual dose of study drug). The number and percentage of subjects achieving SVR₁₂ will be presented along with a two-sided 95% confidence interval (CI) for the percentage.

The normal approximation to the binomial distribution will be used to calculate the CI unless the rate for the primary endpoint is 100%, in which case the Wilson's score method will be used for the calculation of the CI. No hypothesis will be tested.

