8.2 Determination of Sample Size

It is planned to enroll approximately 160 subjects. The sample size for this study is driven by the expected sample size requirements for each genotype and geographical region for this secondary indication. No formal hypothesis is being tested in this study. If

the observed SVR₁₂ rate in this study is 95% among 160 subjects, then the two-sided 95% CI calculated using the normal approximation for a single binomial proportion is 91.6% to 98.4%.

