## **10.3 Primary Efficacy Analysis**

The primary efficacy endpoint is SVR12 (HCV RNA < LLOQ 12 weeks after the last actual dose of study drug). The number and percentage of subjects in the ITT population achieving SVR12 will be summarized with a two-sided 95% CI, calculated using the normal approximation to the binomial distribution. If the SVR12 rate is 100%, then the Wilson's score method will be used to calculate the confidence interval. No hypothesis will be tested.

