## 10.5 Sensitivity Analyses for SVR12

Two-sided 95% CIs for the primary endpoint SVR12 rate will be calculated using both the normal approximation to the binomial distribution and the Wilson score method.

Analyses of the primary endpoint will also be performed on the mITT-GT and mITT-GT-VF populations. Both two-sided 95% normal approximation and Wilson score CIs will be provided for each of these sensitivity analyses.

The analyses described above will also be performed for the geographic region of China.

For each sensitivity analysis, a two-sided 95% CI will be produced only if there are at least 10 subjects in the summary.

Listings of subjects excluded from the mITT-GT and mITT-GT-VF populations will be provided, as applicable.

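### The designated primary SVR12 interval is Wald except at exactly 100%: at n=160 it falls short of 95% coverage at true rates of about 95% to 98.15%, can pass 100%, and gives 159/160 a higher lower limit than 160/160

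*Protocol*

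**What the plan says.** The general rule in Protocol 8.1 is "All statistical tests and confidence intervals will be two-sided with an alpha level of 0.05". For the primary endpoint, Protocol 8.1.2.1 (and the synopsis) states: "The normal approximation to the binomial distribution will be used to calculate the CI unless the rate for the primary endpoint is 100" per cent. SAP 10.3 keeps the same rule; if the observed rate is 100%, "then the Wilson's score method will be used to calculate the confidence interval". Both sections say that no hypothesis will be tested.

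On size, Protocol 8.2 says "It is planned to enroll approximately 160 subjects". For an observed 95% among 160 it adds "then the two-sided 95% CI calculated using the normal approximation for a single binomial proportion is 91.6% to 98.4" per cent. SAP 4.3 repeats this.

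Wilson intervals are planned without condition on the observed rate for the secondary endpoints (Protocol 8.1.2.2, SAP 10.4), for subgroups (Protocol 8.1.2.4, SAP 10.6) and for the additional SVR and relapse endpoints (Protocol 8.1.2.5, SAP 10.7), subject in the last two SAP sections to a minimum of 10 subjects. For the primary rate, SAP 10.5 adds as a sensitivity analysis that intervals "will be calculated using both the normal approximation to the binomial distribution and the Wilson score method", overall and for China.

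**The concern.** With no hypothesis test, the point estimate and its interval are the whole primary efficacy result. In a single-arm study the lower limit is what a reader uses to judge how low the true rate might be. The normal approximation is weakest for proportions close to 1, and this trial is expected to land there. The exception at 100% deals with the one outcome where the Wald interval has zero width. It leaves the neighbouring outcomes untouched and creates a break between 159 and 160 responders. At stake are an interval labelled 95% that does not deliver 95%, upper limits that cannot be true, and a lower limit that falls when one more subject responds.

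**Working it through.** **Inputs.** n = 160 and the illustrative 95% (Protocol 8.2); two-sided 95%, z = 1.960 (Protocol 8.1); Wald below 100% and Wilson at 100% (Protocol 8.1.2.1, SAP 10.3); cirrhosis results from Protocol Tables 6 and 8; planned genotype mix from Protocol 5.1.

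**Formulas**, with p = x/n:
- Wald: p ± z·√(p(1−p)/n).
- Wilson: [p + z²/2n ± z·√(p(1−p)/n + z²/4n²)] / (1 + z²/n).
- Exact coverage at true rate π: the sum of the Binomial(160, π) probabilities of every x whose interval contains π.

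**1. The plan's figure.** For 152/160, √(0.95×0.05/160) = 0.01723 and 1.960×0.01723 = 0.0338, giving 91.62% to 98.38%. This matches the stated 91.6% to 98.4%. Wilson for the same result: centre (0.95 + 0.0120)/1.0240 = 0.9394, half-width 0.0350, giving 90.4% to 97.4%.

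**2. Where the rate is likely to fall.** Tables 6 and 8, subjects with cirrhosis: GT1 98/101, GT2 35/35, GT4 20/20, GT5 2/2, GT6 7/7, GT3 naïve 64/65, GT3 experienced 48/51.
- Pooled: 274/281 = 97.5%.
- Weighted to 90 GT1, 46 GT2 and 24 others, the others at the pooled GT3 rate of 112/116: (87.33 + 46 + 23.17)/160 = 97.8%.
- The same with all 24 others responding: (87.33 + 46 + 24)/160 = 98.3%.

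The genotype split within the 24 is not given, hence the range.

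**3. Limits near the top of the range (n = 160).**

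| Responders | Wald | Wilson | Difference in lower limit |
|---|---|---|---|
| 152 | 91.62 to 98.38 | 90.44 to 97.44 | 1.18 |
| 156 | 95.08 to 99.92 | 93.75 to 99.02 | 1.33 |
| 157 | 96.02 to 100.23 | 94.63 to 99.36 | 1.39 |
| 158 | 97.03 to 100.47 | 95.56 to 99.66 | 1.47 |
| 159 | 98.15 to 100.60 | 96.55 to 99.89 | 1.61 |
| 160 | (rule switches to Wilson) | 97.66 to 100 | – |

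At 160/160 the Wilson lower limit is n/(n + z²) = 160/163.84 = 97.66%. The 160th responder therefore lowers the reported limit by 98.15 − 97.66, about 0.5 points. At a true rate of 98% the chance of 157 to 159 responders, and so of an upper limit above 100%, is 56%.

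**4. Exact coverage of the planned rule (n = 160).**

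| True rate | Planned rule | Lower limit too high | Wilson throughout |
|---|---|---|---|
| 95% | 89.9% | 9.4% | 95.7% |
| 96% | 88.1% | 11.4% | 96.1% |
| 97% | 85.8% | 13.9% | 96.9% |
| 97.5% | 90.9% | 8.9% | 93.4% |
| 98% | 86.6% | 12.9% | 95.7% |
| 98.15% | 84.5% | 15.2% | 97.0% |
| 98.2% | 99.7% | 0 | 97.3% |
| 99% | 99.9% | 0 | 97.7% |

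The nominal share for a lower limit that is too high is 2.5%. At 98% the whole 12.9% comes from one outcome, exactly 159 responders: 160 × 0.98¹⁵⁹ × 0.02 = 0.129. Once the true rate passes 98.15%, the 159/160 interval contains it and coverage jumps by about 15 points.

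Coverage moves up and down between the tabulated rates. On a fine grid from 95% to 98.15% the planned rule runs from 84.5% to 95.1%, mean about 90.9%. Wilson runs from 93.0% to 97.7%, mean 95.4%.

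**The case against.** The strongest answer is that the better interval is already pre-specified. SAP 10.5 reports Wilson beside Wald for the primary rate, overall and for China, and SAP 10.5.1 does so for the imputation analyses. A reader of the study report will see both. No margin, threshold or success criterion rests on either, the point estimate is unchanged, and the sample size was set by genotype and regional needs. All of this stands, and it limits the severity. It does not remove the point: SAP 10.3 still names the Wald interval as primary, and the documents give no reason for treating this endpoint differently from the Wilson-based secondary and subgroup rates.

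Some stronger readings are tempting, but the documents do not support them:
- A reader might infer that the lower limit is always too high. It is not: above about 98.15% the rule over-covers, and the inferred range of 97.5% to 98.3% straddles that point.
- A reader might carry the 100% switch over to China. It is stated only for the primary ITT analysis. For China, SAP 10.5 gives both intervals, and SAP 10.6 gives a Wilson interval for region as a subgroup.
- A reader might call this the weakest interval in the plan. SAP 10.9 uses the normal approximation for the fatigue-score proportion with no fallback at 0% or 100%.
- A reader might take 91.6% to 98.4% as an arithmetic error. It is right for the method named.

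The reversal also has limited reach: it bites only if all 160 respond, which has probability 3.9% at a true rate of 98%. Limits above 100% could be truncated for display without changing coverage.

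**Conclusion.** The concern holds in a limited form. With 160 subjects the designated primary interval covers the truth about 84% to 91% of the time at the true rates checked from 95% to 98.15%, with most misses on the favourable side; it over-covers above that. It gives impossible upper limits for 157 to 159 responders and a reversed ordering between 159 and 160.

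The limits and the reversal depend only on n = 160 and the stated rule. The coverage figures also depend on the true rate. The range of 97.5% to 98.3% is inferred from earlier cirrhosis data and an assumed genotype split; no section states it as the planning rate. The shortfall is already present at the protocol's illustrative 95%.

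A reader might conclude that this must be fixed before the trial can be interpreted. The documents do not support that, because no hypothesis or threshold depends on the interval and the Wilson interval will be reported anyway. It should be fixed.

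**What to change.** In Protocol 8.1.2.1, the synopsis and SAP 10.3, make the two-sided 95% Wilson score interval primary for SVR12 at every observed rate and delete the switch at 100%. Keep the Wald interval as the supplementary display in SAP 10.5. In Protocol 8.2 and SAP 4.3, restate the precision for 152/160 as 90.4% to 97.4%.

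This removes the limits above 100% and the reversal, brings coverage close to nominal, and matches the secondary endpoints. Wilson is not perfect: its coverage also varies, with a low of 93.0% on the grid from 95% to 98.15%, and its misses lean towards upper limits that are too low.

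The cost is wording and one planning figure; the Wilson calculation is already planned for this endpoint. The reported lower limit becomes about 1.2 to 1.6 points less favourable for 152 to 159 responders, so the change should be settled before the SVR12 results are seen.

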8.1.2.2 Secondary Efficacy Endpoints

The secondary efficacy endpoints are:

- The percentage of subjects with on-treatment HCV virologic failure (defined as confirmed increase of > 1 log₁₀ IU/mL above nadir during treatment, confirmed HCV RNA ≥ 100 IU/mL after HCV RNA < LLOQ during treatment, or HCV RNA ≥ LLOQ at the end of treatment with at least 6 weeks of treatment), and
- The percentage of subjects with post-treatment relapse (defined as confirmed HCV RNA ≥ LLOQ between end of treatment and 12 weeks after the last dose of study drug among subjects who completed treatment as planned with HCV RNA < LLOQ at the end of treatment, excluding re-infection), and
- The percentage of HCV/HIV co-infected subjects (determined at Screening) achieving SVR₁₂.

For the analysis of relapse, a subject enrolled to receive 12 weeks of treatment is considered to have completed treatment if study drug duration is 77 days or more, and a subject enrolled to receive 16 weeks of treatment is considered to have completed treatment if study drug duration is 105 days or more.

The percentages of subjects with on-treatment virologic failure, post-treatment relapse, and SVR₁₂ will be calculated along with two-sided 95% Wilson score confidence intervals.

In addition, a summary of reason for SVR₁₂ non-response (e.g., on-treatment virologic failure, relapse, re-infection) will be provided for the set of all subjects and for the set of HCV/HIV co-infected subjects.

8.1.2.3 Sensitivity Analysis

As sensitivity analyses, the percentage of subjects in the mITT-GT and mITT-GT-VF populations achieving SVR₁₂, as applicable, will be summarized.

8.1.2.4 Subgroup Analysis

The percentage of subjects with SVR₁₂ will be calculated, as will the corresponding two-sided 95% Wilson score CIs, for subgroups based on the following factors for the ITT and mITT population(s):

- Geographic region;
- HCV genotype and available subtype;
- Prior HCV treatment history;
- For treatment-experienced subjects, type of prior treatment experience;
- For treatment-experienced subjects, type of non-response to previous treatment;
- Baseline HIV co-infection status;
- IL28B genotype;
- Sex;
- Age;
- Type of Asian descent;
- Baseline BMI;
- Baseline HCV RNA levels;
- Baseline HOMA-IR;

- Baseline platelet count;
- Baseline albumin;
- Baseline GGT;
- Baseline LDL;
- Baseline APRI;
- Baseline FIB-4;
- Baseline AST/ALT ratio;
- Baseline alpha fetoprotein (AFP);
- Baseline Child-Pugh Score;
- Baseline AFP, platelet count and albumin;
- History of diabetes;
- History of bleeding disorders;
- History of depression or bipolar disorder;
- Baseline metabolic syndrome;
- History of cardiovascular disease;
- Injection drug use;
- Baseline stable opiate substitution use;
- Baseline hepato-protectant medication use;
- Study drug compliance.

Further details about subgroup analyses will be described in the Statistical Analysis Plan (SAP).

8.1.2.5 Additional Efficacy Endpoints

The following additional efficacy endpoints will be summarized:

- The percentage of subjects with HCV RNA < LLOQ at each post-baseline visit in the Treatment Period (using data as observed);
- The percentage of subjects with SVR₄;
- The percentage of subjects with SVR₂₄;

- A summary of reason for SVR₄ and SVR₂₄ non-response (e.g., on-treatment virologic failure, relapse, re-infection);
- The percentage of subjects who relapsed after achieving SVR₁₂.

In the above analyses for SVR and relapse, the percentage of subjects will be calculated along with a two-sided 95% Wilson score confidence interval. The summaries listed above will also be presented by geographic region.

Additionally, the secondary endpoints will be summarized by geographic region, and the subgroup and sensitivity analyses will be performed separately for each geographic region.

The additional endpoints along with the secondary endpoints of on-treatment virologic failure and post-treatment relapse will also be summarized for the HCV/HIV co-infected subjects. The sensitivity analyses will also be performed for the HCV/HIV co-infected population.

